## **5.4 Method for Assigning Subjects to Treatment Groups**

In general, the patient should be randomized as soon as possible after the baseline evaluation is completed. Randomization should be completed and study drug started on the day of evaluation.

### **5.4.1 Stratification**

Prior to randomization, subjects will be stratified on thrombotic risk based on the presence of one or more of the following characteristics: deep vs. muscular venous thrombosis, postoperative status, and single vs. multiple venous segment involvement.

### **5.4.2 Central Automated Randomization**

Subjects will be randomized in 1:1 ratio to either apixaban group or placebo group. The randomization scheme will be generated by the study statistician.

## **5.5 Preparation and Administration of Study Drug**

Drug (apixaban or matching placebo) will be stored and distributed from McKesson to each of the 3 study sites. This study uses a double blind design. Specifically, McKesson will pre-package the doses of either apixaban or matching placebo into bottles labeled with assigned bottle numbers, and then dispense a three month supply of the drug to the Mayo Clinic Pharmacy at each study site.

Upon randomization, the Mayo Clinic Pharmacy (MCP) at each site will be informed of the subject's allocation. The MCP pharmacist will then dispense the drug (apixaban or matching placebo) according to randomized assigned bottle number in a three month's supply (200 tablets/bottle). The study coordinator will then go to MCP, retrieve the drug and hand it to the patient. The first dose will be given to the patient immediately upon receiving the medication. Three month's supply will be provided to the patient.

For the initial 7 days, subjects will take 2 tablets (apixaban or matching placebo) twice daily (total of 4 tablets per day). Thereafter patients will take one tablet twice daily (apixaban 5 mg or matching placebo). Drug labeling will be according to national law and GMP ruling Annex 13.19. Active study drug and placebo will be stored at 15-25°C (59-77°F).

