### **3 Study Design**

#### **3.1 General Design**

This is a Single center, multi-Mayo site, randomized, double-blind, placebo-controlled, superiority clinical trial. Major bleeding and clinically relevant non-major bleeding will also be evaluated. Subjects will be screened at both outpatient clinic visit appointments or during hospitalization using direct referrals or by daily automated electronic screening of vascular radiology ultrasound and computed tomography reports. The baseline ultrasound will be clinical indicated, obtained for this purpose, and will be carefully reviewed by study personnel. Interested qualified subjects will be consented and offered participation in this trial. Pre-randomization anticoagulation treatment for cDVT is allowed up to a maximum of 72 hours. After randomization, patients allocated to apixaban will receive 10 mg twice daily for 7 days, followed by 5 mg twice daily for 3 months. Patients allocated to placebo control will receive twice daily matching placebo tablets in a similar fashion. All patients will undergo serial ultrasound imaging at 7 days, 14 days and 90 days. Patients developing symptomatic DVT or PE will be evaluated by cross-sectional imaging (ultrasound or computed tomography (CTA)) appropriate for their symptom assessment as part of their standard care. Allocation to treatment will be done centrally. Once consent has been obtained, clinically indicated baseline laboratory values will be confirmed (drawn within past 4 weeks) and subjects will begin treatment and follow-up for 3 months.

The primary composite efficacy endpoint of this study will be a composite of thrombus propagation, pulmonary embolism (PE), symptomatic VTE recurrence including recurrent DVT, PE or all cause fatality. The primary safety outcome will be major bleeding and clinically relevant non-major bleeding (ISTH criteria; 21). All suspected recurrent VTE, deaths, as well as all episodes of bleeding and vascular events will be evaluated by a central, blinded, independent adjudication committee. Adjudication results will be the basis for the final analyses.

There will be two secondary endpoints. The first will assess the timing of thrombus propagation relative to the original date of diagnosis for those individuals who experience a thrombus propagation. The second will be an assessment of net clinical benefit or harm assessed as the composite of the primary efficacy outcome or the principal safety outcome up to day 90.

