### **HIGHLY EFFECTIVE METHODS OF CONTRACEPTION**

- Male condoms with spermicide
- Hormonal methods of contraception including combined oral contraceptive pills, vaginal ring, injectables, implants and intrauterine devices (IUDs) such as Mirena® by WOCBP subject or male subject's WOCBP partner.
- Female partners of male subjects participating in the study may use hormone based contraceptives as one of the acceptable methods of contraception since they will not be receiving study drug,
- IUDs such as ParaGard®,
- Tubal ligation
- Vasectomy.
- Complete Abstinence\*

\*Complete abstinence is defined as complete avoidance of heterosexual intercourse and is an acceptable form of contraception for all study drugs.

Acceptable alternate methods of highly effective contraception must be discussed in the event that the subject chooses to forego complete abstinence

2. Acute co-existing proximal DVT (popliteal, femoral, iliac veins or IVC), pulmonary embolism, splanchnic vein thrombosis, cerebral venous sinus thrombosis within the past 3 months for whom anticoagulation therapy is indicated.
3. Age < 18 years.
4. Continuous treatment with therapeutic anticoagulant for more than 72 hours pre-randomization.
5. Contraindication to anticoagulant therapy
6. Significant kidney disease. Creatinine clearance < 25 ml/min using the Cockcroft-Gault equation:  $GFR = (140\text{-age}) * (\text{Wt in kg}) * (0.85 \text{ if female}) / (72 * \text{Cr})$ . (within last four weeks)
7. Significant liver disease (e.g. acute hepatitis, chronic active hepatitis, cirrhosis) or ALT (or AST) > 3 x ULN. (within last four weeks)
8. Platelet count <  $50 \times 10^9 / \text{L}$ . (within last four weeks)
9. Life expectancy < 12 months.
10. Current active bleeding.
11. Concomitant use of strong CYP3A4 inhibitors (e.g., HIV protease inhibitors, systemic ketoconazole) or strong CYP 3A4 inducers like rifampicin.
12. Active cancer defined as any evidence of cancer on cross-sectional imaging or cancer treatments within the past 6 months (chemotherapy, radiation therapy or cancer related surgery).
13. Anticipated need for urgent/emergent surgery or major invasive procedure.

14. Dual antiplatelet therapy (thienopyridine plus aspirin) and/or aspirin greater than 165 mg while on study medication.

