### **4.3 Subject Recruitment, Enrollment and Screening**

This is a multi-Mayo center, randomized, double blind, placebo controlled, superiority trial for efficacy. Experienced data management personnel enroll patients, collect clinical trial data and ensure quality control. Patient registration occurs using centralized registration and randomization systems to ensure patient eligibility. The Research Radiology Core provides radiological image management including a centralized system of image collection, archiving and review for clinical studies. The Research Pharmacy Core offers a central pharmacy service, along with quality-control systems for medication order fulfillment, shipment and reconciliation.

Patients will be recruited from two potential sources, hospital in-patients and outpatients attending anticoagulation clinics at one of three sites: Mayo Clinic Rochester, Mayo Clinic Eau Claire, or Mayo Clinic La Crosse. Upon subject identification, the study will be explained in detail by the investigators or study coordinator, the consent form reviewed, questions answered, and the consent form signed.

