#### **5.2 Treatment Regimen**

Patients randomized to apixaban will be treated with 10 mg twice daily for 7 days followed by 5 mg twice daily for 3 months. Patients assigned to matching placebo will take their tablets in a similar fashion.

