### **Subject Compliance Monitoring**

Study medication should be used in accordance with the protocol, under the responsibility of the investigator. The research pharmacist or any authorized person should maintain a complete and accurate record of the receipt of all study medication supplied to the site by McKesson. These records should include dates of receipt, batches and quantities received. The sponsor will provide bulk drug supply to McKesson. McKesson will then package "open label" stock drug in bottles containing 200 tablets of either apixaban or matching placebo. Upon request, each site will then be supplied with open label drug in bottles. Upon receipt of drug from McKesson, each Mayo Clinic Pharmacy site will coordinate the randomization received by the statistician and label the bottle and dispense blinded prescription bottle to study coordinator. The study coordinator will then disperse drug to the subject.

Sites will be supplied enough study drug to complete half of their assigned recruitment target. Recruitment targets are as follows: Rochester (150 patients), La Crosse (50 patients), Eau Claire (50 patients). Once each site is nearing half of their recruitment target, then they will request additional drug from McKesson. This shipment plan will help to redistribute available drug to the sites most actively recruiting.

Record keeping at each site MCP will include subject number, the date, quantity and batch numbers of the dispensed and returned medication and the dispenser. All non-dispensed medication supplied to the site by McKesson should be kept securely in the original containers in a designated locked container until retrieved/dispensed.

Subjects should be instructed to return all used, partially used, or unused medication packaging to the site.

A log should be kept by subject number, of the date, quantity, and batch numbers returned (the dispensing and the return log may be combined). For medication supplied to the site by McKesson, the total amount of medication used and unused should equal the amount received, any discrepancies should be explained in writing. All unused medication will be destroyed and records of shipment/receipt and or destruction will be maintained.

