## **5.6 Prior and Concomitant Therapy**

Non-steroid anti-inflammatory drugs (NSAIDs) and antiplatelet agents are discouraged. However, if indicated, aspirin up to a dosage of 165 mg/day will be allowed. Dual antiplatelet therapy (P2Y12 inhibitor plus aspirin) and/or aspirin greater than 165 mg are not permitted.

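### The first study dose is ordered immediately on receipt, with no switching rule for patients who may already have had up to 72 hours of therapeutic anticoagulation

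*Combined protocol and SAP*

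**What the plan says.** All references are to the combined protocol and SAP.

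- **Prior treatment is allowed.** Section 3.1: "Pre-randomization anticoagulation treatment for cDVT is allowed up to a maximum of 72 hours". Exclusion criterion 4 in section 4.2 removes only patients with "Continuous treatment with therapeutic anticoagulant for more than 72 hours pre-randomization". A patient who took a full therapeutic dose that morning can therefore be eligible.
- **The start is fast.** Section 5.4: "Randomization should be completed and study drug started on the day of evaluation". Section 5.5: "The first dose will be given to the patient immediately upon receiving the medication". Section 5.8.3 carries the same sentence.
- **The first dose is the loading dose.** Under 5.2 apixaban patients are "treated with 10 mg twice daily for 7 days". Section 5.5 makes this two 5 mg tablets per dose, or the same number of placebo tablets.
- **The section on prior therapy does not cover the switch.** Section 5.6 begins "Non-steroid anti-inflammatory drugs (NSAIDs) and antiplatelet agents are discouraged" and deals otherwise only with aspirin and dual antiplatelet therapy.
- **Responsibility for drug use.** Under Subject Compliance Monitoring in 5.5: "Study medication should be used in accordance with the protocol, under the responsibility of the investigator".

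No section sets a minimum gap, says when open-label anticoagulation stops, or ties the first study dose to the prior agent's schedule.

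**The concern.** Two instructions that are reasonable apart do not fit together. The plan admits patients who may still have a therapeutic anticoagulant on board, then orders a 10 mg loading dose as soon as the bottle is handed over. In the apixaban arm this can stack one anticoagulant dose on another. In the placebo arm it cannot.

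Prior treatment is plausible here, because section 4.3 recruits from "hospital in-patients and outpatients attending anticoagulation clinics". The documents do not say how common it is.

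What is at stake is a short, avoidable extra exposure with no planned benefit, in a trial whose second primary objective is bleeding. Eligible patients may have creatinine clearance as low as 25 ml/min or platelets as low as 50 x 10^9/L (section 4.2), and postoperative status is a stratification factor (5.4.1).

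**Working it through.** **Reading the text.** The plan gives no figure on this point, so there is none to reproduce; the sample size of 121 per arm does not depend on it. Set side by side, 3.1 and exclusion 4 permit recent therapeutic dosing, 5.4 asks for a same-day start, and 5.5 and 5.8.3 ask for dose 1 at handover. The late-dose rule at the end of 5.5 concerns study medication only. The Day 0 row for concurrent medications in the section 6.2 schedule would capture the prior agent, but no time of last dose is asked for there or in Appendix B1.

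**Illustration of size.** Inputs:

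- Half-life about 12 hours (section 1.2).
- Study dose 10 mg every 12 hours in week 1 (5.2, 5.5).
- Assumed, not in the documents: the prior agent is apixaban 10 mg every 12 hours, with *n* prior doses and a gap of *t* hours from the last one to study dose 1. Absorption is ignored. That is rough, since section 1.2 puts the peak at 4 hours.

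Formulas:

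- Planned week-1 steady-state amount just after a dose: 10 / (1 - 0.5) = 20 mg.
- Amount just after the *n*th prior dose: 20 x (1 - 0.5^n), which gives 10.0, 15.0, 17.5 and 19.69 mg for *n* = 1, 2, 3 and 6. Six doses, at hours 0 to 60, are the most that fit before hour 72.
- Amount just after study dose 1: that value x 0.5^(t/12) + 10. The factor is 1, 0.794, 0.707 and 0.5 at 0, 4, 6 and 12 hours.

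| Prior doses | Gap 0 h (extreme) | Gap 4 h | Gap 6 h | Gap 12 h |
|---|---|---|---|---|
| 1 | 20.0 mg (0%) | 17.9 mg (-10%) | 17.1 mg (-15%) | 15.0 mg |
| 2 | 25.0 mg (+25%) | 21.9 mg (+10%) | 20.6 mg (+3%) | 17.5 mg |
| 3 | 27.5 mg (+38%) | 23.9 mg (+19%) | 22.4 mg (+12%) | 18.8 mg |
| 6 | 29.7 mg (+48%) | 25.6 mg (+28%) | 23.9 mg (+20%) | 19.8 mg |

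Percentages are against 20 mg. One prior dose never exceeds the planned amount, and several can. Waiting the full 12 hours never exceeds it.

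**Duration.** With six prior doses and a 4-hour gap, the amount stays above 20 mg for 12 x log2(25.63 / 20) = 4.3 hours after dose 1. The excess halves every 12 hours: just after dose 2 the amount is 25.63 x 0.5 + 10 = 22.8 mg, 14% above planned. The stacking happens once, among about 90 x 2 = 180 dosing occasions.

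**Comparison with what the plan already accepts.** Under the late-dose rule in 5.5, a missed dose is taken as soon as possible the same day and the schedule resumes. Take a week-1 patient at steady state whose dose is 8 hours late and whose next dose is on time. After the late dose: 20 x 0.5^(20/12) + 10 = 6.3 + 10 = 16.3 mg. Four hours later: 16.3 x 0.794 + 10 = 22.9 mg, 15% above planned. That is more than the two-dose case at 4 hours and less than the three-dose case.

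**The case against.** The strongest reply is that this is a drafting matter that sites will manage.

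- **Sites have room within the text.** The word immediately runs from the patient receiving the bottle, which follows randomisation and a pharmacy trip. A site could time handover to the next due dose, at least for a twice-daily agent. *This stands in part.* It shows that overlap can be avoided, but the plan does not ask anyone to avoid it. An investigator who holds the dose after handover departs from the written instruction.
- **The size depends on assumed inputs.** The 28% figure needs a particular agent, six prior doses and a 4-hour gap. Two prior doses at 6 hours give 3%. *This stands.* The figures show direction and rough scale only.
- **The plan already tolerates similar peaks under its late-dose rule.** *This stands for the smaller cases*, and it caps the importance of the point. That rule deals with unplanned lapses; here the protocol itself sets the timing.
- **The prior agent is already recorded** under Day 0 concurrent medications. *This stands.* Only the dose times are missing.

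A reader might go further and infer that the plan requires overlapping anticoagulation, or that the overlap will distort the bleeding comparison. The documents support neither. They allow overlap without ordering it. Without the share pre-treated, the agents used or the gaps, no number of excess bleeds can be derived.

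**Conclusion.** The point holds as a low-priority patient-safety clarification. Sections 5.5 and 5.8.3 state a dosing rule that, followed literally, can stack doses in pre-treated apixaban patients, and no other section corrects it.

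The excess comes from the timing of one dose and fades within a few dosing intervals in the illustration. Its size is unknown. Agents other than apixaban were not sized, and a longer-interval agent could overlap for longer. The sample size, alpha levels, power and analysis sets do not change, and there is no basis for expecting a different trial conclusion.

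**What to change.** In 5.5 and 5.8.3, replace the first-dose sentence with a rule applied alike in both arms:

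- Open-label anticoagulation stops at randomisation.
- Patients with no prior anticoagulant take dose 1 at once.
- Pre-treated patients take dose 1 when the next dose of the prior agent would have been due, or when a heparin infusion is stopped. For LMWH plus warfarin, the LMWH schedule sets the time.
- A vitamin K antagonist is left to the investigator, using any INR already available clinically. No study test is added, since INR is not among the Day 0 laboratory values in 6.1.

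Add a line to 5.4 letting the same-day start yield to this rule. Record the time of the last prior dose and the time of the first study dose.

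**Cost:** a few sentences, one cross-reference and two data fields. Some first doses will be delayed by hours, up to about a day after a once-daily agent, and will be taken without staff present. Because the rule does not depend on allocation, it does not disturb the blind.

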### **Subject Compliance Monitoring**

Study medication should be used in accordance with the protocol, under the responsibility of the investigator. The research pharmacist or any authorized person should maintain a complete and accurate record of the receipt of all study medication supplied to the site by McKesson. These records should include dates of receipt, batches and quantities received. The sponsor will provide bulk drug supply to McKesson. McKesson will then package "open label" stock drug in bottles containing 200 tablets of either apixaban or matching placebo. Upon request, each site will then be supplied with open label drug in bottles. Upon receipt of drug from McKesson, each Mayo Clinic Pharmacy site will coordinate the randomization received by the statistician and label the bottle and dispense blinded prescription bottle to study coordinator. The study coordinator will then disperse drug to the subject.

Sites will be supplied enough study drug to complete half of their assigned recruitment target. Recruitment targets are as follows: Rochester (150 patients), La Crosse (50 patients), Eau Claire (50 patients). Once each site is nearing half of their recruitment target, then they will request additional drug from McKesson. This shipment plan will help to redistribute available drug to the sites most actively recruiting.

Record keeping at each site MCP will include subject number, the date, quantity and batch numbers of the dispensed and returned medication and the dispenser. All non-dispensed medication supplied to the site by McKesson should be kept securely in the original containers in a designated locked container until retrieved/dispensed.

Subjects should be instructed to return all used, partially used, or unused medication packaging to the site.

A log should be kept by subject number, of the date, quantity, and batch numbers returned (the dispensing and the return log may be combined). For medication supplied to the site by McKesson, the total amount of medication used and unused should equal the amount received, any discrepancies should be explained in writing. All unused medication will be destroyed and records of shipment/receipt and or destruction will be maintained.

If a dose of study medication (apixaban or matching placebo) is not taken at the scheduled time, the dose should be taken as soon as possible on the same day and the prescribed dosing schedule should be resumed. The dose should not be doubled to make up for missed doses.

## **5.6 Prior and Concomitant Therapy**

Non-steroid anti-inflammatory drugs (NSAIDs) and antiplatelet agents are discouraged. However, if indicated, aspirin up to a dosage of 165 mg/day will be allowed. Dual antiplatelet therapy (P2Y12 inhibitor plus aspirin) and/or aspirin greater than 165 mg are not permitted.

## **5.7 Packaging**

Apixaban (5 mg tablet strength or matching placebo control) will be provided in a HDPE-bottle containing 200 tablets to complete a total of 3 months of therapy.

## **5.8 Blinding of Study**

This is a double blind placebo controlled study.

### **5.8.1 Receipt of Drug Supplies**

The BMS/Pfizer will provide bulk drug supply to McKesson. McKesson will then package drug pre-labeled by assigned randomization bottle numbers in bottles containing 200 tablets of either apixaban or matching placebo to each site. Upon request, each site will then be supplied with drug in bottles, along with a shipment manifest of the total bottle numbers dispensed. Upon receipt of drug from McKesson, each Mayo Clinic Pharmacy site will coordinate the dispensing of the blinded randomized treatment to study coordinator. Upon receipt of the study treatment supplies, an inventory must be performed and a drug receipt log filled out by the person accepting the shipment at MCP. The designated study staff will count and verify that the shipment contains all the items noted in the shipping invoice. Any discrepancies, damaged or unusable study drug in a given shipment (active drug or comparator) will be documented in the study files. The sponsor-investigator will be notified immediately of any discrepancies, damaged or unusable products that are received. Delegated unblinded study staff will have access to the randomization key. Through use of a Mayo licensed randomization software, the bottle numbers will be assigned to the designated site at the time of randomization using the stratification outlined in 5.4.1.

### **5.8.2 Storage**

Apixaban (and matching placebo control) will be stored at MCRP 15-25°C (59-77°F).

### **5.8.3 Dispensing of Study Drug**

Upon randomization, the MCP will be informed of the subject's allocation. The MCP research pharmacist will then assemble the drug in a three month's supply. The study coordinator will then go to MCP, retrieve the drug and hand it to the patient. The first dose will be given to the patient immediately upon receiving the medication. Apixaban 5 mg (or matching placebo) will be provided in a HDPE-bottle containing 200 tablets.

Regular study drug reconciliation should be performed to document drug assigned, drug dispensed, drug returns, and drug remaining. This reconciliation should be logged on the drug reconciliation form, and signed and dated by the study team.

